SAR Serious Adverse Reaction

SER Spherical Equivalent Refractive Error

SD Standard Deviation

SOPs Standard Operating Procedures
SSAR Suspected Serious Adverse Reaction

SUSAR Suspected Unexpected Serious Adverse Reaction

TMF Trial Master File

TMG Trial Management Group
TSC Trial Steering Committee
UAR Unexpected Adverse Reaction

VA Visual Acuity

Doc No: ST06-RD01 Page **4** of **47**

1. BACKGROUND AND DESIGN

Atropine 1% is very effective in slowing myopia progression, but it is not popular because of its unwanted side effects of pupillary dilation and cycloplegia and possible rebound effect. Atropine eye drops at a concentration of 0.01% are expected to be safe and well tolerated. This is supported by evidence from other trials that have employed the same and other more potent anti-muscarinic agents (e.g. 1% atropine; pirenzepine), and the well-established safety profile of atropine use in ophthalmology.

This is a multicentre, randomised, double-masked, placebo-controlled, superiority trial, with 2:1 allocation of intervention and control (atropine: placebo).

1.1 Research Hypothesis

Our hypothesis is that low dose atropine eye drops will reduce myopia progression in children compared with placebo.

1.2 Study Aim

The aim of the study is to evaluate the efficacy and safety of low dose atropine (0.01%) eye drops to reduce progression of myopia in UK children.

1.3 Study Objectives

The primary objective is:

 To evaluate the efficacy of 0.01% atropine eye drops to reduce the progression of myopia in children after 24 months of treatment.

The secondary objectives are:

- To evaluate the safety and tolerability of low dose atropine eye drops in terms of difficulties with near vision and reading, local discomfort and stinging of eye drops, photophobia, and occurrence of allergic reactions.
- To determine the mechanism of action of atropine eye drops. Specifically, we will evaluate if atropine has an effect on central axial length of the eye, position of the lens, peripheral retinal defocus and use of spectacle correction.

The exploratory objectives are:

• To explore the influence of other factors in the progression of myopia, including accommodation, chorio-retinal thickness at the macula, peripheral axial length, hours of outdoor activity, iris colour, ethnicity, and family history.

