2.2 Secondary outcome measures

- Central axial length: measured using a laser biometer at central fixation conditions
- Best corrected distance visual acuity (BCdVA) (uniocular and binocular): assessed using the logMAR ETDRS chart. This is a standard letter chart used in research to ensure accuracy and validity of the acuity measurements and has been shown to be repeatable in children
- Near visual acuity (VA) (uniocular and binocular): tested using near logMAR ETDRS at 40 cm
- Reading speed: measured with the Wilkins Rate of Reading test
- Pupil diameter: measured using an autorefractor
- Spectacle correction
- Tolerability: using a 4-point scale to quantify, from the point of view of the participant, (1) local irritation/stinging associated with eye drop instillation;
 - (2) photophobia; and
 - (3) difficulties reading and writing
- Adverse event rates and allergic reactions rates
- Quality of Life: measured using the EQ-5D-Y

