7.2 Secondary outcomes

For the secondary outcome analyses, results will be used from both eyes to investigate if atropine has an effect on the following endpoints at month 24; central axial length, pupil diameter, uniocular BCdVA and uniocular near VA. Each of these endpoints will be compared between the atropine and placebo groups using GEE and 95% CIs and will be adjusted for the corresponding baseline secondary outcomes (if available).

For the following endpoints at month 24; binocular BCdVA, binocular near VA, reading speed, and quality of life (i.e. EQ-5D-Y VAS and Index) comparisons between the atropine and placebo groups will be performed using analysis of covariance (ANCOVA) and 95% CIs and will be adjusted for the corresponding baseline secondary outcome (if available). Tolerability at month 24 will be compared between the atropine and placebo groups using an independent samples t-test. Spectacle correction at month 24 will be compared between the atropine and placebo groups using the chi-square test (or Fisher's exact test if appropriate). N(%) of spectacle correction (all day and sometimes) will also be presented by treatment arm.

The number of AEs, ARs, SAE, SARs, SUSARs and number (%) of patients experiencing these events will be reported. The chi-square test (or Fisher's exact test if appropriate) will be used to check whether incidences of adverse events differ between the treatment groups. Risk ratio and 95% CIs will be reported.

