7.5 Additional analyses

Additional analyses will be performed on the primary and secondary outcomes to investigate any differences between atropine and placebo groups at all other available time points not previously analysed (i.e. 6, 12 and 18 months). The primary and secondary outcomes at baseline will only be presented by treatment arm in the PP analysis in this additional analyses, as the ITT baseline results are presented in the baseline characteristics table.

For the primary outcome SER, results will be used from both eyes and will be compared using GEE (repeated measures model) and 95% CIs and will be adjusted for baseline SER. Secondary analysis of the primary outcome will be adjusted for baseline SER and minimisation variables (i.e. site and ethnicity), baseline age and history of parental myopia (at least one parent).

For the secondary outcome analyses, results will be used from both eyes to investigate if atropine has an effect on the following endpoints; central axial length, pupil diameter, uniocular BCdVA and uniocular near VA. These endpoints will be compared between the two groups using GEE (repeated measures model) and 95% CIs and will be adjusted for the corresponding baseline secondary outcomes (if available). For the following endpoints; binocular BCdVA, binocular near VA, reading speed and quality of life (i.e. EQ-5D-Y VAS and Index) comparisons between the two groups will be performed using repeated measures ANCOVA and 95% CIs and will be adjusted for the corresponding baseline secondary outcome (if available).

Tolerability will be compared between the atropine and placebo groups using repeated measures ANOVA and 95% CI. Spectacle correction will be compared between the atropine and placebo groups using repeated measures generalised linear model. N(%) of spectacle correction (all day and sometimes) will also be presented by treatment arm.

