- Tolerability stingy at month 24: mean (SD) by treatment arm, difference in means with 95% CI, p-value from independent t-test, in ITT and PP analysis.
- Tolerability itchiness at month 24: mean (SD) by treatment arm, difference in means with 95% CI, p-value from independent t-test, in ITT and PP analysis.
- Tolerability blurry vision at month 24: mean (SD) by treatment arm, difference in means with 95% CI, p-value from independent t-test, in ITT and PP analysis.
- Tolerability sore eyes at month 24: mean (SD) by treatment arm, difference in means with 95% CI, p-value from independent t-test, in ITT and PP analysis.
- Tolerability difficult to read/write at month 24: mean (SD) by treatment arm, difference in means with 95% CI, p-value from independent t-test, in ITT and PP analysis.

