8.10 Toxicity/ Symptoms

- AEs, no.events (%) by treatment arm, no. patients(%) by treatment arm, Risk ratio with 95% CI and p value
- ARs, no.events (%) by treatment arm, no. patients(%) by treatment arm, Risk ratio with 95% CI and p value
- SARs, no. events (%) by treatment arm, no. patients (%) by treatment arm, Risk ratio with 95% CI and p value
- UARs, no. events (%) by treatment arm, no. patients (%) by treatment arm, Risk ratio with 95% CI and p value
- SAEs, no. events (%) by treatment arm, no. patients (%) by treatment arm, Risk ratio with 95% CI and p value
- SUSARs, no. events (%) by treatment arm, no. patients (%) by treatment arm, Risk ratio with 95% CI and p value

Fatal AEs/SAEs, no. events (%) by treatment arm, no. patients (%) by treatment arm, Risk ratio with 95% CI and p value

AEs, ARs, SAEs, SARs, UARs and SUSARs will also be presented by system organ class.

Doc No: ST06-RD01 Page **21** of **47**

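### Photophobia and allergic reaction rates are named in the safety objective and as secondary outcomes, but no named item analysis or table row reports either

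*Supplement*

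**What the plan says.** Section 1.3 of the SAP sets a secondary objective on safety and tolerability and names its content: "difficulties with near vision and reading, local discomfort and stinging of eye drops, photophobia, and occurrence of allergic reactions".

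Section 2.2 turns these into secondary outcomes. Tolerability is rated by the participant on a 4-point scale with three components: local irritation or stinging, photophobia (listed as "2) photophobia; and"), and trouble with reading and writing. A separate bullet lists "Adverse event rates and allergic reactions rates".

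The analysis principles are generic on tolerability. Section 7.2 says "Tolerability at month 24 will be compared between the atropine and placebo groups using an independent samples t-test". Section 7.5 says "Tolerability will be compared between the atropine and placebo groups using repeated measures" ANOVA for the other visits. Neither names any item.

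The analysis details are itemised. Section 8.5 lists six tolerability analyses, the last being "Tolerability difficult to read/write at month 24". Section 8.8 repeats the same six for months 6, 12 and 18. For safety, 8.10 lists the regulatory event categories and adds that "AEs, ARs, SAEs, SARs, UARs and SUSARs will also be presented by system organ class".

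**The concern.** The itemised lists in Section 8 and the table shells are what an analyst will program from. They do not match the outcomes defined in 2.2. The other two tolerability components, stinging and reading/writing, each have a named analysis and a table row; photophobia has neither. Allergic reactions are set beside adverse event rates in 2.2 as a rate of their own, but the safety section gives no definition, count or row for them.

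Two parts of the safety objective would then have no identifiable result. The alternative is that someone chooses a stand-in item for photophobia, or a grouping of allergic terms, after the data have been seen. For a trial whose aim covers safety as well as efficacy, that choice should be fixed beforehand.

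**Working it through.** The plan gives no figure to reproduce here. The check traces each named outcome from objective to table.

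**Photophobia**
- 1.3: named in the objective ("photophobia, and occurrence of allergic reactions").
- 2.2: named as the second tolerability component.
- 7.2 and 7.5: not named; included only if the word tolerability is read through the definition in 2.2.
- 8.5 (month 24): six items, namely *eye feels*, *stingy*, *itchiness*, *blurry vision*, *sore eyes* and *difficult to read/write*. None is labelled photophobia or light sensitivity.
- 8.8 (months 6, 12, 18): the same six.
- Appendix 1, main clinical outcomes table and other-time-points table: the same six.

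Count of specified item comparisons:
- 8.5: 6 items × 1 visit × 2 populations (ITT, PP) = 12.
- 8.8: 6 items × 3 visits × 2 populations = 36.
- Total: 12 + 36 = 48, of which 0 are labelled photophobia.

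This count describes coverage only. It says nothing about bias, power or error rates.

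**Allergic reactions**
- 1.3: named in the objective.
- 2.2: named as a rate.
- 7.2: the categories are AEs, ARs, SAEs, SARs and SUSARs. Section 4 defines AR as adverse reaction, so the abbreviation does not stand for allergic reaction.
- 8.10: seven lines (AEs, ARs, SARs, UARs, SAEs, SUSARs, fatal events); 0 for allergic reactions.
- Appendix 1, safety table: seven rows; 0 for allergic reactions.
- Appendix 1, system organ class table: six event blocks, each with five named classes and an open row. That is 6 × 5 = 30 named rows, 0 of them for allergic reactions.

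**Can the rate be recovered from the safety tables?** An allergic event would be counted in the AE total, in the AR total if related to the drops, and under some system organ class. Allergic events can fall under more than one class, so neither the totals nor the class rows isolate the rate listed in 2.2.

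**Are the data collected?** Table 1 of the SAP schedules tolerability and adverse events at 6, 12, 18 and 24 months. It does not list the questionnaire items.

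**The case against.** The strongest case is that both outcomes are covered already. Section 2.2 makes photophobia part of tolerability, and 7.2 and 7.5 say tolerability will be compared. Allergic reactions are adverse events by definition, so they enter counts by arm with risk ratios and confidence intervals. The class table is plainly illustrative: it has open rows and does not even pre-print eye disorders. The questionnaires are held in the Trial Master File and the protocol is not shown, so *eye feels* may be a shortened label for the light-sensitivity question.

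Much of this stands, and it rules out several stronger readings.

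- A reader might infer that no analysis covers either outcome, or that the data would be lost. The documents do not support that: the generic wording reaches photophobia, and allergic events remain within the adverse event counts.
- A reader might infer that photophobia was never asked about. Without the questionnaire this cannot be known.
- A reader might infer that photophobia was chosen to capture the burden of pupil dilation. Section 1 attributes pupil dilation to 1% atropine, expects the trial's 0.01% to be well tolerated, and does not link dilation to photophobia. Pupil diameter also has its own analysis.
- A reader might infer that all the unfamiliar items fall outside 2.2. Itchiness may be local irritation, and blurry vision may relate to the near-vision part of the objective in 1.3.

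The mismatch itself remains. A generic sentence does not tell the analyst to report an item that every explicit list leaves out. An unseparated event count is not the rate named in 2.2. If *eye feels* is the photophobia item, the SAP does not say so, and linking outcomes to analyses is the SAP's task.

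**Conclusion.** The point holds as a gap between outcome definition and specified reporting. Following Section 8 and the shells as written gives no identified photophobia comparison (0 of 48 item comparisons) and no allergic reaction rate (0 of 7 lines in 8.10, 0 of 7 safety table rows). It affects two named parts of one secondary safety objective and leaves the primary analysis untouched. It should be corrected, but it is not critical to the trial's main conclusion.

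The photophobia half assumes that *eye feels* is not the light-sensitivity item. If it is, the fault reduces to an unclear label that still needs correcting. The allergic reaction half does not depend on that assumption.

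**What to change.** 1. **Photophobia.** Check the questionnaire and do one of three things. If a photophobia item exists, add it to 8.5, 8.8 and both outcome tables. If one of the six listed items measures it, label that item as photophobia throughout. If no such item was collected, say so in the SAP and report photophobia from coded adverse event terms.
2. **Allergic reactions.** Add a row to 8.10 and the safety table giving events, patients, risk ratio and 95% CI by arm. Identify the events from a list of coded terms fixed before unmasking.
3. **Mapping.** State which component of 2.2 each of the six analysed items represents. Mark as additional only those that map to none.

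The cost is SAP wording, a few table rows and a few extra comparisons. No new data collection is needed: the allergic row uses adverse event data already scheduled, and each photophobia route uses data already held.

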1.4 Inclusion and Exclusion Criteria

Patients will be eligible to participate in the study if they fulfil the following criteria below. Eligibility will be confirmed by a medically qualified doctor and documented on the eligibility checklist form.

Inclusion Criteria

- 1. Age 6-12 years (at the time of consenting)
- 2. Myopia of -0.5D or greater (spherical equivalent refractive error) in both eyes
- 3. Best-corrected distance visual acuity (BCDVA) 0.20 logMAR or better in both eyes

Exclusion Criteria

- 1. Children with other ocular morbidities
- 2. Myopia of -10D or greater in either eye
- 3. Astigmatism of 2D or higher in either eye
- 4. Amblyopia
- Significant health problems that can compromise the ability to attend research visits or complete the trial
- 6. Other factors that may compromise the ability to attend the research appointments
- 7. Parents or children with poor understanding of the English language
- 8. Children enrolled in other interventional trials*
- 9. Allergy or hypersensitivity to atropine or excipients
- 10. Previous use of atropine eye-drops, prior or current use of Ortho-K contact lenses or contact lenses with dual focus, multifocal or extended depth of focus lens design
- 11. Children or Parents / Guardians with latex allergy as the dropper used to administer the eye-drop contains latex

*Children enrolled in observational studies are potential candidates for CHAMP UK. Whether or not children enrolled in CHAMP UK are also involved in other observational studies is at the discretion of the CHAMP UK local Principal Investigator (PI) and should be considered when the burden on participants is not expected to be onerous. Coenrolment with other studies should be documented in the Case Report Form (CRF).

Full details of the background to the trial and its design are presented in the protocol.

Doc No: ST06-RD01 Page **6** of **47**

2. OUTCOME MEASURES

2.1 Primary outcome measure(s)

• The primary outcome is spherical equivalent refractive error (SER) (i.e. myopia severity) of both eyes after 24 months measured by autorefractor under cycloplegia, adjusted for baseline.

2.2 Secondary outcome measures

- Central axial length: measured using a laser biometer at central fixation conditions
- Best corrected distance visual acuity (BCdVA) (uniocular and binocular): assessed using the logMAR ETDRS chart. This is a standard letter chart used in research to ensure accuracy and validity of the acuity measurements and has been shown to be repeatable in children
- Near visual acuity (VA) (uniocular and binocular): tested using near logMAR ETDRS at 40 cm
- Reading speed: measured with the Wilkins Rate of Reading test
- Pupil diameter: measured using an autorefractor
- Spectacle correction
- Tolerability: using a 4-point scale to quantify, from the point of view of the participant, (1) local irritation/stinging associated with eye drop instillation;
 - (2) photophobia; and
 - (3) difficulties reading and writing
- Adverse event rates and allergic reactions rates
- Quality of Life: measured using the EQ-5D-Y

2.3 Exploratory Outcomes/Mechanistic Evaluations*

- Peripheral axial length: measured using a laser biometer at peripheral fixation conditions
- Peripheral retinal defocus: measured with the autorefractor at central and peripheral fixation conditions
- Anterior chamber depth: measured with a laser biometer
- Accommodation: using a near target and in accordance with the Clinical Assessment Guidelines
- Iris colour: measured using a visual grading scale of dark brown, light brown, blue, green, grey
- Height and weight to provide information about the links between the child's development and eye growth and potentially information about lifestyle
- Hours of outdoor activity: measured using an activities questionnaire
- Ciliary body biometry: measured using anterior-segment OCT (AS-OCT). This will enable
 changes in lens position and ciliary muscle changes resulting from atropine use to be compared
 with normal myopic growth
- Chorio-retinal thickness: measured using spectral domain OCT (SR-OCT). This will enable differences in choroidal thickness resulting from atropine use to be compared with normal myopic growth

*Only to be carried out in sites with the relevant equipment. If measurements for exploratory outcomes cannot be collected this will not be recorded as a protocol deviation.

Doc No: ST06-RD01 Page **7** of **47**

3. DATA

3.1 CRF Forms and variables

Full details of data collection and timing are described in the trial protocol (Version 5.0 08/12/2020). A copy of the CRFs and questionnaires are presented in the Trial Master File (TMF).

3.2 Management of datasets

Below is the standard policy for management of data in the CTU as given in the CTU SOPs, at the time of analysis (including DMEC reports/Interim analysis (if required)):

 If the CTU is providing the Data Management for the study then the Data Manager in collaboration with the Study Statistician will extract data from MACRO following procedures as detailed in the SOP DM09 Database Closure/Lock and the corresponding study Data Management Plan (DMP).

The trial database will be stored in MACRO:

- DMEC reports: In collaboration with the Statistician, the Data Manager will create MACRO output files to support the analysis. This will act as the frozen dataset. It is the responsibility of the statistician to accurately record the date of freezing and ensure all data is retrieved. If there are no errors, the study database will be re-opened for further data entry.
- If there are errors, the Study Statistician will report these to the Data Manager. The Data Manager in consultation with the Study Statistician, Data Project Manager and Senior Statistician will resolve the errors and determine which of the database closure activities are required to be undertaken. The Data Manager will re-create the MACRO output files to support the analysis. Database closure & lock: The same process for DMEC reporting will be followed for database closure and lock, the only difference being when the MACRO output files are created and there are no errors found for final analysis, the database should be locked as per SOP DM09.

3.3 Data completion schedule

Participants will be followed every six months for a total of five trial visits as outlined in accordance with the schedule of assessments as shown in Table 1:

Doc No: ST06-RD01 Page **8** of **47**

Table 1: Schedule of Assessments for the CHAMP UK Study

	Baseline	6	12	18	24
		months	months	months	months
Consent	✓				
Randomisation	✓				
Medical history (including height*,					
weight*, concomitant medications	✓	✓	✓	✓	✓
and spectacle correction)					
Severity of parental myopia (self-	√				
report)	ŕ				
Adverse events		✓	✓	✓	✓
Tolerability		✓	✓	✓	✓
EQ-5D-Y questionnaire	✓	✓	✓	✓	✓
Activities questionnaire- to be sent	✓	✓	✓	✓	✓
home with participant for completion					
Best corrected VA (logMAR ETDRS)	✓	✓	√	√	✓
Near VA (near logMAR ETDRS)	✓	✓	✓	✓	✓
Iris colour	✓				
Reading speed (Wilkins Rate of Reading Test)	✓	✓	✓	✓	✓
Pupil diameter prior to cycloplegia	✓	✓	✓	✓	✓
Accommodation (in accordance with guideline)*	✓	✓	✓	✓	✓
Peripheral retinal defocus (autorefractor)*	✓		✓		✓
Anterior chamber depth (laser biometer)*	✓		✓		✓
Cycloplegic refractive error (autorefractor)	✓	✓	✓	✓	✓
Ciliary body biometry (AS-OCT)*	✓		✓		✓
Central axial length (laser biometer)	✓	✓	✓	✓	✓
Peripheral axial length (laser biometer)*	✓		✓		✓
Chorio-retinal thickness (SD-OCT)*	✓	✓	✓	✓	✓
MEMS data		✓	√	√	✓
Study drug dispensing	✓	✓	✓	✓	

3.4 Data verification

Data verification, consistency and range checks will have been performed at the data entry stage by the CTU, as well as checks for missing data (copies can be found in the TMF) according to SOP DM04. Additional range, consistency and missing data checks will be performed, as appropriate, when the analysis is performed (and when the datasets for analysis are constructed). All variables will be examined for unusual, outlying, unlabelled or inconsistent values.

Given the thorough nature of our follow-up procedure we expect the issue of missing data to be relatively minimal. We anticipate high compliance with initial data collection as this is close to the time of patient registration.

If any clinical data is missing for the primary outcome at 24 months, imputation will be carried out by imputing extreme values of change within treatment arm (i.e. smallest and largest change from the previous time point to 24 months) in a sensitivity analysis. If the baseline primary outcome is missing, spectacle refraction will be used in the sensitivity analysis.

Study drug adherence will be self-reported and the event logs will be extracted from the MEMS during visits via a device connected to the computer to assess study drug adherence.

Any problems with trial data will be queried with the Trial Managers, Data Managers, or statisticians, as appropriate. If possible, data queries will be resolved, although it is accepted that due to administrative reasons and data availability a small number of problems will continue to exist. This will be minimised.

